Duration of Study Participation	Enrollment will occur over approximately a 6 month-period. Every participant will complete baseline questionnaires and wear an ambulatory ECG patch for up to 7 days. Every participant will receive an app notification to complete a web-based Patient Reported Outcomes (PRO) survey 15 and 60 days following enrollment. Participation in the study will end after completion of the 60 day PRO survey or after 90 days, whichever date is earlier.
Number of Participants	Approximately 2600 participants will be enrolled

This document contains information that is privileged or confidential and may not be disclosed unless such disclosure is required by applicable laws and regulations. The information in this document is the property of Apple Inc. and may not be reproduced, published, or disclosed to others without written authorization from Apple Inc.

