7.12 Participants that may be excluded from specific analyses

Participants may be excluded from some analyses for incomplete data or for various other reasons. The reasons may include:

1. Failure to contact Study Telehealth Provider within 30 days of enrollment.
2. Failure to be deemed eligible for ePatch wear due to emergent symptoms, determined at Study Visit #1.
3. Failure to return an ePatch within 45 days of enrollment.
4. Failure to begin wearing ePatch within 14 days of patch shipment
5. Failure to verify at Study Visit #1 that the participant had a cohort classification as either (1) Irregular Rhythm Notification, or status of (2) Afib or (3) Inconclusive via the ECG app (i.e., with at least 1 ECG recorded within the 14 days before study enrollment indicating classification of either AFib or Inconclusive, where the latter is defined as “Inconclusive,” “Heart Rate Over 120,” or “Heart Rate Under 50”)
6. Withdrawal from the study per Section 9.0

This document contains information that is privileged or confidential and may not be disclosed unless such disclosure is required by applicable laws and regulations. The information in this document is the property of Apple Inc. and may not be reproduced, published, or disclosed to others without written authorization from Apple Inc.

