9.0 WITHDRAWAL

Every participant should be encouraged to remain in the study until they have completed the protocol-required follow-up period. If the participant withdraws prematurely from the study, the reason for withdrawal should be documented. Possible reasons for premature withdrawal may include, but are not limited to the following:

- Withdrawal of consent: participant decides to withdraw from the study for any reason. This may be concluded if/when a participant taps the withdraw button within the app or asks to be withdrawn.
- Investigators believe it is in the best interest of the participant to discontinue the study, for any reason.
- It is discovered that participant does not meet inclusion/exclusion criteria

Withdrawal Process:

Participants will have the option to withdraw from the study by tapping a “Withdraw from Study” button within the app. This will disable notifications and will result in a cessation of data collection. If a participant calls the Study Telehealth Provider requesting withdrawal from the study, the Study Telehealth Provider will instruct the participant how to initiate withdrawal on the app. It will not be possible for any party other than the study participant themselves to withdraw from the study. In the few cases where the participant has initiated contact with the Study Telehealth Provider, and thereafter selects “Withdraw from Study” on the app, they may still receive follow-up communication from the Study Telehealth Provider. In order to stop further communication, these participants would need to inform the Study Telehealth Provider Team that they wish to be withdrawn.

Once withdrawn, participants would be able to re-enroll only by reinstalling the application, but will be considered a new study participant without linkage to their prior data.

The following will be considered lost-to-follow-up:

- Death of the participant
- Lost/stolen iPhone and/or Apple Watch

This document contains information that is privileged or confidential and may not be disclosed unless such disclosure is required by applicable laws and regulations. The information in this document is the property of Apple Inc. and may not be reproduced, published, or disclosed to others without written authorization from Apple Inc.

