10.0 STATISTICAL CONSIDERATIONS

10.1 Analysis Sets

All analyses will be reported for the overall cohort, as well as by cohort status determined at enrollment: (1) Irregular Rhythm Notification, and status of (2) Afib or (3) Inconclusive via the ECG app (i.e., with at least 1 ECG recorded within the 14 days before study enrollment indicating classification of either AFib or Inconclusive, where the latter is defined as “Inconclusive,” “Heart Rate Over 120,” or “Heart Rate Under 50”).

The Full Analysis Set (FAS) will consist of all enrolled participants who complete the informed consent process. This analysis set will be used to summarize subject demographics, medical history, adverse events, self-reported health status, diagnosis, and contact with the health care provider.

The ePatch eligible analysis set (EEAS) will consist of those in the FAS deemed eligible to receive an ePatch at Study Visit #1.

The ePatch Analysis Set (EAS) will consist of all those in the EEAS who receive and return an ePatch with at least 1 hour of usable data and who do not belong to the Fallout Group.

The Fallout Subgroup Analysis Set (FOG) will consist of participants meeting the criteria of Section 7.10. Demographic and medical history information will be presented for this analysis set.

Objectives 1a, 1b, and 2b and 2c will be conducted using the EAS, whereas Objective 2a will be conducted using the EEAS. The analyses for Objectives 1a, 1b, and 2b and 2c will be repeated in the EEAS as a sensitivity analysis using appropriate methods for handling missing data.

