3. ANALYSIS SETS

The Full Analysis Set (FAS) will consist of all enrolled participants who complete the informed consent process. This analysis set will be used to summarize subject demographics, medical history, adverse events, self-reported health status, diagnosis, and contact with the health care provider.

The ePatch Eligibility Analysis Set (EEAS) will consist of those in the FAS deemed eligible to receive an ePatch at Study Visit #1. This analysis set will be used to assess Objective 2a.

The ePatch Analysis Set (EAS) will consist of all those in the EEAS who receive and return an ePatch with at least 1 hour of usable data and who do not belong to the Fallout Subgroup. This analysis set will be used to assess Objectives 1a, 1b, and 2b and 2c. We will repeat these analyses in the EEAS as a sensitivity analysis using appropriate methods for handling missing data.

The Fallout Subgroup Analysis Set (FOG) will consist of participants who enroll and complete the informed consent process but otherwise do not complete the study. Reasons for study incompleteness include; failure to contact Study Telehealth Provider within 30 days of enrollment, being deemed ineligible at Study Visit #1 for ePatch wear due to emergent symptoms, ePatch not returned within 45 days of enrollment, failure to start wearing ePatch within 14 days of shipment, unable to verify at Study Visit #1 a study eligible IRN or ECG-app notification, study withdrawal (i.e., withdrawal of consent), or lost to follow-up (i.e., death). We will present demographic and medical history information for this analysis set.

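### SAP 3 leaves participants with a timely, usable patch out of the primary AF estimates if they later withdraw or die, which conflicts with SAP 4.6 and 4.7

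*Combined protocol and SAP*

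**What the plan says.** - **EAS.** SAP 3 admits those in the ePatch eligibility set (EEAS) "who receive and return an ePatch with at least 1 hour of usable data and who do not belong to the Fallout Subgroup". Protocol 10.1 has the same two conditions: "with at least 1 hour of usable data and who do not belong to the Fallout Group". The EAS serves Objectives 1a, 1b, 2b and 2c.
- **Fallout Subgroup.** SAP 3 defines it as "participants who enroll and complete the informed consent process but otherwise do not complete the study". The listed reasons end with "study withdrawal (i.e., withdrawal of consent), or lost to follow-up (i.e., death"). Three of the other reasons carry a time limit (30, 45 and 14 days) and two are settled at Study Visit #1. Withdrawal and loss to follow-up have neither.
- **Protocol counterpart.** Item 6 of protocol 7.12 is "Withdrawal from the study per Section 9.0", also untimed, in a list of people who may be excluded from some analyses. Protocol 10.1 points to section 7.10 for the fallout criteria, but 7.10 is the time and events schedule; the list is in 7.12.
- **Loss to follow-up.** Protocol 9.0 counts two events: "Death of the participant" and "Lost/stolen iPhone and/or Apple Watch". SAP 3 mentions only death.
- **Follow-up.** The synopsis says "Participation in the study will end after completion of the 60 day PRO survey or after 90 days, whichever date is earlier".
- **Missing data.** SAP 4.6 treats patch data as missing when there is under 1 hour of analyzable wear or no return within 45 days. SAP 4.7 explains omission from these four objectives by the absence of analyzable monitoring data.

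**The concern.** The outcome for these four objectives is fixed once the patch has been worn and returned. What a participant does afterwards adds nothing to it. Making EAS membership depend on later events therefore removes observed outcomes from both numerator and denominator.

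The removal can also depend on the result. Study Visit #2 discloses the patch finding while follow-up is still running. Someone told that no AF was found may see less reason to stay, and someone who dies may be more likely to have had AF. These mechanisms push the estimate in opposite directions, so the sign of any bias cannot be predicted. Objectives 1a and 1b are the primary objectives, and the usable patches lost in this way are the ones the 400-per-group target is meant to secure.

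**Working it through.** **1. The plan's own precision figure.** SAP 1.3 promises a 95% CI no wider than 0.10 with 400 returned patches. The Gaussian width at p = 0.5 is 2 × 1.96 × √(0.25/n):
- n = 400: 0.0980, which meets 0.10.
- n = 300: 0.1132 (SAP: 11.3%).
- n = 200: 0.1386 (SAP: 13.9%).

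All three reproduce. The exact (Clopper-Pearson) width at n = 400 is 0.1002.

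**2. Is there time for an exclusion after the outcome?** Protocol 7.4.2 expects most patches back by about days 14–20 and sets day 45 as the limit. Protocol 7.6 expects Study Visit #2 on days 15–45. The 60-day questionnaire opens on day 60, and participation ends when it is completed or at day 90, whichever is earlier.
- Patch back on day 20, questionnaire completed on day 60: 60 − 20 = 40 days still at risk.
- Patch back on day 45, questionnaire completed on day 60: 60 − 45 = 15 days.
- Outer limit, day 14 to day 90: 76 days.

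**3. One case under each section.** Take a participant with a usable patch returned on day 20 who withdraws consent, or dies, on day 50.

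| Section | Treatment |
|---|---|
| SAP 3, Fallout Subgroup | Member, because the reason has no time limit |
| SAP 3 and protocol 10.1, EAS | Not included |
| SAP 4.6 | Patch data not missing |
| SAP 4.7 | Not among those described as omitted |
| SAP 3, EEAS sensitivity analysis | Included, with an observed result |

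No section returns this person to the primary analysis.

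**4. Size.** Let p be the AF proportion among all valid, timely patches, w the share of those later withdrawn or lost, and q the AF proportion in that share. The documents give none of the three.

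EAS estimate = (p − w·q)/(1 − w), so shift = [w/(1 − w)] × (p − q).

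The middle columns start from 400 valid patches; widths are at p = q = 0.5.

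| w | Shift if q is 20 points from p | n left of 400 | Gaussian width | Exact width | Shift at p = 0.30, q from 0 to 1 |
|---|---|---|---|---|---|
| 1% | ±0.20 points | 396 | 0.0985 | 0.1007 | +0.30 to −0.71 |
| 2% | ±0.41 | 392 | 0.0990 | 0.1012 | +0.61 to −1.43 |
| 5% | ±1.05 | 380 | 0.1005 | 0.1028 | +1.58 to −3.68 |
| 10% | ±2.22 | 360 | 0.1033 | 0.1057 | +3.33 to −7.78 |

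If q = p there is no shift and only n falls. For scale, the planned half-width at n = 400 is 0.0980/2 = 4.9 points.

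**5. Worked example with assumed rates.** Take 400 valid patches, 200 with AF.
- If 2% of AF-positive and 10% of AF-negative participants leave: 196/(196 + 180) = 196/376 = 52.1%.
- With the rates reversed: 180/376 = 47.9%.
- The exact width goes from 0.1002 at n = 400 to 0.1033 at n = 376.

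**The case against.** The best defence is that the plan does not intend this. SAP 4.7 speaks only of people without patch data. Protocol 7.4.2 uses the fall-out label only for late return, late start or non-return. Protocol 7.12 is permissive, and the other five reasons in SAP 3 are all failures to obtain an eligible, timely patch. That shows what was probably meant, but SAP 3 is categorical and is the text a programmer will follow.

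A second defence is the EEAS repeat. It stands in part: that set does not exclude the Fallout Subgroup, so these patches can be used there. It remains a sensitivity analysis, though, and it also handles other missing data, so it neither replaces the primary estimate nor isolates this exclusion.

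Third, the numbers may be small. The loss rates are assumed, withdrawal takes a deliberate action in the app, and the loss of precision is slight. This stands.

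Fourth, whether data may be used after consent is withdrawn depends on consent terms that are not available here. Protocol 9.0 says that withdrawal stops data collection and is silent on data already held; silence is not permission. This stands for withdrawals, but not for deaths.

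A reader might go further and infer that anyone who leaves the 60-day questionnaire unanswered also falls out of the EAS, since such a person has not completed the study. The documents do not support that. Non-response is not among the fallout reasons in SAP 3 or protocol 7.12, SAP 4.6 handles it as missing data, and SAP 4.3 expects that some fallout members will have completed the questionnaire.

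**Conclusion.** The point holds as a conflict within the SAP that worsens the primary estimate if SAP 3 is applied as written. It affects Objectives 1a, 1b, 2b and 2c. Objective 2a uses the EEAS and is not affected.

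The likely effect is modest and of unknown direction: about 0.2 to 1.1 points at 1% to 5% loss if AF prevalence differs by 20 points in those lost, and 2.2 points at 10%. Larger shifts need both substantial loss and a stronger link with AF. These figures rest on assumed values of w and q.

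Two further readings go too far. The recorded result is not erased; it is left out of the primary estimate and remains available to the sensitivity analysis. And loss of a device is not an exclusion in the SAP's own words: it enters only if the protocol 9.0 definition of loss to follow-up is read into SAP 3, which names death alone.

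The change is worth making before analysis because it settles who is in the primary set at almost no cost.

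**What to change.** In SAP 3, and in protocol 7.12 item 6 and 10.1, limit the reason to: *withdrawal, death or other loss to follow-up before return of an ePatch with at least 1 hour of usable data*. Add that a later death, device loss or withdrawal does not remove a participant from the EAS, with data collected before withdrawal of consent kept as far as the consent terms allow. Say whether device loss counts as loss to follow-up in the SAP, and correct the cross-reference in protocol 10.1 from 7.10 to 7.12. SAP 4.6 and 4.7 then agree with SAP 3 and need no change.

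The cost is about one sentence in each place and no new data. There is one small downside: protocol 9.0 lets a withdrawn participant re-enrol as a new participant without linkage to the earlier record, so someone who withdraws after a valid patch and re-enrols could be counted twice. This should be rare.

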4. ANALYSIS METHODS

4.1 General Principles

Method for Constructing Confidence Intervals

We will construct confidence intervals using the asymptotic Gaussian approximation. For proportions near 1 or 0, a potential drawback of this method is confidence intervals containing values outside of the range [0,1]. If we encounter confidence intervals with bounds outside of the [0,1] range we will instead construct the confidence intervals using the bias corrected and accelerated (BCa) method of creating a bootstrap confidence interval.

Incomplete Dates

If only the year of a date is given (YY), then the date shall be set to 'YY0701'. If only the year and month of a date is given (YYMM), then the date shall be set to 'YYMM15'.

Descriptive Statistics

Numerical variables will be summarized using standard summary statistics including the number of participants, mean, standard deviation, median, 10th and 90th percentile and range (i.e., minimum and maximum) as appropriate. For categorical data, proportions will be presented in a frequency table format.

Multiple Patches per Participant

In rare instances where a single user ID is associated with data available from more than one patch, only data from the final patch will be used in statistical analyses.

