10.3 Statistical Approaches to Outcome Analyses

This document contains information that is privileged or confidential and may not be disclosed unless such disclosure is required by applicable laws and regulations. The information in this document is the property of Apple Inc. and may not be reproduced, published, or disclosed to others without written authorization from Apple Inc.

There are no pre-specified statistical hypotheses in this clinical study. Descriptive statistics and 95% confidence intervals will be presented using available data as detailed below.

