10.3.3 Subgroup Analyses

The proportions and 95% confidence intervals for the primary outcomes (study objectives 1a and 1b) will be performed separately by age group (<55, 55-64, ≥ 65), sex, and race/ethnicity, cohort status determined at enrollment, and cohort status determined throughout the observations period (e.g., received an IRN during patch wear, received an ECG app-Inconclusive classification during patch wear). Chi-squared tests will be performed to determine if these proportions differ significantly by subgroup.

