1.3 Number of Participants Needed to Address Objectives

This clinical study is not designed to test any pre-specified statistical hypotheses. Because all participants enrolling in this clinical trial will either have received an IRN or an ECG app-AFib classification, we derived the number of enrolled participants needed to achieve our desired precision for addressing Objectives 1a and 1b.

To obtain a 95% confidence interval (CI) with a width no greater than 0.10 when addressing Objective 1a we will require 400 IRN participants that are exclusively in the IRN group (i.e., who do not enter the study via the ECG app), who are deemed eligible for ePatch receipt and who return their ePatches. Similarly, for Objective 1b to obtain a 95% CI with a width no greater than 0.10 we will require 400 participants who exclusively enroll via the ECG-app classification of AFib, who are deemed eligible for ePatch receipt and who return their ePatches.

The figure above displays the 95% CI width for the target sample size of 400 (over the range of possible AF percents we could observe) and three sample sizes that represent a failure to meet the target; n=350 (87.5% of target), n=300 (75% of target) and n=200 (50% of target). The height of the lines (the vertical axis) correspond to the CI width. The horizontal axis corresponds to the percent AF observed. As noted 400 patches (the blue line) will ensure the estimated CIs are no wider than 10%. The lines representing a failure to meet the target number of returned ePatches for each group shows at worst the CI could be as wide as 13.9% at 50% of the target and a percent with AF of 50%. However, even at 87.5% or even 75% of the recruitment target the worst case is a CI width of 11.3% and in both cases a modest amount of possible AF percentages will yield a CI with a width < 10%.

If, after enrolling 500 participants, we observe that there is 50% overlap or greater between participants who enroll through both the IRN and the ECG app, we will modify our targeted enrollment with the understanding that the reporting of findings will be accompanied with a detailed context of the types of subjects that contribute to both estimates addressing Objectives 1a and 1b.

Allowing for an approximate attrition rate of 35% and an overlap of 50% between participant types (IRN vs ECG-app) we calculated a minimum target enrollment of 2600 participants.

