4.3 Analysis Methods

Analysis of the Primary Endpoint Addressing Objective 1a and 1b

For Objectives 1a and 1b we have designed the study to estimate the proportion of participants diagnosed with AF within a 0.10 confidence interval width.

Objective 1a – The proportion of participants with an IRN prior to enrollment who have AF confirmed by ambulatory ECG patch monitoring.

This proportion will be estimated as the ratio of the number of participants in the EAS who have atrial fibrillation or atrial flutter of at least 30 seconds duration on patch wear and received an IRN before enrollment, divided by the number of participants in the EAS who received an IRN before enrollment. An exact 95% two-sided confidence interval will also be presented. We will also describe the number of participants who received an IRN before or during enrollment with arrhythmias other than atrial fibrillation.

Objective 1b Analysis – The proportion of participants with an ECG app-AFib classification prior to enrollment who have AF confirmed by ambulatory ECG patch monitoring.

This proportion will be estimated as the ratio of the number of participants in the EAS who have atrial fibrillation or atrial flutter of at least 30 seconds duration on patch wear and received an ECG app-AFib classification before enrollment divided by the number of participants in the EAS who received an ECG app-AFib classification before enrollment. An exact 95% two-sided confidence interval will also be presented. We will also describe the number of participants who received an ECG app-Fib before enrollment with arrhythmias other than atrial fibrillation.

Analysis of the Secondary Endpoints Addressing Objectives 2a, 2b and 2c

Objective 2a Analysis - The proportion of participants with an IRN or ECG app-AFib classification reporting contact with a non-study healthcare provider at 15 and 60 days after study enrollment.

This proportion will be estimated as the ratio of the number of participants who received an IRN or ECG app-AFib classification in the EEAS who reported contact with a non-study healthcare provider at 15 (and separately at 60) days after study enrollment divided by the number of participants in the EEAS who received an IRN or ECG app-AFib. An exact 95% two-sided confidence interval will also be presented.

Objective 2b Analysis

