This proportion will be estimated as the ratio of the number of participants in the EAS who have atrial fibrillation or atrial flutter of at least 30 seconds duration on patch wear and received an ECG app-Inconclusive status before enrollment, divided by the number of participants in the EAS who received an ECG app-Inconclusive status before enrollment. An exact 95% two-sided confidence interval will also be presented. We will also describe the

number of participants who received an ECG app-Inconclusive status before enrollment with arrhythmias other than atrial fibrillation.

Objective 2c Analysis

This proportion will be estimated as the ratio of the number of participants who have atrial fibrillation or atrial flutter of at least 30 seconds duration on patch wear who are greater than 65 years of age at enrollment divided by the number of participants enrolled who are greater than 65 years of age at enrollment using the EAS. An exact 95% two-sided confidence interval will also be presented. We will also describe the number of participants who are 65 years of age or older at enrollment with arrhythmias other than atrial fibrillation. A similar proportion will be presented for those less than 65 years of age at enrollment.

Sensitivity and Sub-analyses

The proportions and 95% confidence intervals for Objectives 1a and 1b will be performed separately by age group (<55, 55-64, ≥ 65), sex, race/ethnicity, cohort status determined at enrollment, cohort status determined during patch wear (e.g., received an IRN during patch wear, received an ECG app-Inconclusive classification during patch wear) and selected medical history conditions (e.g., ever diagnosed you with atrial fibrillation or atrial flutter, or ever had a stroke, Transient Ischemic Attack (TIA) or “Mini Stroke”). Chi-squared tests will be performed to determine if proportions differ significantly by subgroup.

Baseline demographics and medical history, survey results, and adverse events will be summarized using descriptive statistics for the FAS. Baseline demographics and medical history will also be summarized for participants in the FOG.

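### The SAP prescribes two interval methods for the same proportions; its general rule gives a zero-width interval when no participant, or every participant, in a cell has AF

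*Combined protocol and SAP*

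**What the plan says.** **General rule.** SAP 4.1 says: "We will construct confidence intervals using the asymptotic Gaussian approximation". It recognises trouble for proportions near 0 or 1 and adds a switch: "If we encounter confidence intervals with bounds outside of the [0,1] range we will instead construct" them by the BCa bootstrap. The rule is not limited to particular analyses.

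**Objectives.** SAP 4.3 says for each of Objectives 1a, 1b, 2a, 2b and 2c: "An exact 95% two-sided confidence interval will also be presented". Protocol 10.3.1 and 10.3.2 say the same.

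**Subgroups.** SAP 4.3 (Sensitivity and Sub-analyses) says: "The proportions and 95% confidence intervals for Objectives 1a and 1b will be performed separately by age group", and goes on to other factors. Protocol 10.3.3 is parallel: "The proportions and 95% confidence intervals for the primary outcomes (study objectives 1a and 1b) will be performed separately by age group". Neither names a method. The protocol's lead-in at 10.3 says: "Descriptive statistics and 95% confidence intervals will be presented using available data as detailed below".

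**Precision.** SAP 1.3 claims a width of at most 10% with 400 patches per group. For shortfalls it states "the worst case is a CI width of 11.3"% (down to 75% of target) and "at worst the CI could be as wide as 13.9% at 50% of the target".

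**The concern.** Two methods are prescribed for the same proportions, with no sentence giving precedence. SAP 4.1 cannot be read as a rule for other kinds of estimate, because it discusses proportions explicitly.

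The gap matters most in the subgroups of Objectives 1a and 1b. One analyst could carry the exact method over from the parent objective while another applies the general rule in 4.1. They would then report different intervals from the same counts.

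The 4.1 rule also fails in the situation its fallback was written for. A cell with no AF, or with AF in everyone, would be reported with no uncertainty. Small cells are plausible: SAP Table 2 lists nine race/ethnicity response options and a non-binary gender category, and SAP 4.3 also splits by cohort status during patch wear and by selected medical history.

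**Working it through.** **Inputs.** From SAP 1.3: n = 400, 350, 300 and 200, with stated widths of at most 10% (n = 400), 11.3% (n = 300) and 13.9% (n = 200). From SAP 4.1: the Gaussian rule and its [0,1] trigger. The documents give no subgroup sizes or AF proportions, so the values used in steps 3 and 4 are assumptions.

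**1. Reproducing the stated widths.** The Gaussian width at p = 0.5 is 2 × 1.96 × √(0.25/n). The exact (Clopper-Pearson) limits for x/n are the 2.5% quantile of Beta(x, n−x+1) and the 97.5% quantile of Beta(x+1, n−x); the table gives the largest width over all x.

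| n | Stated | Gaussian | Exact |
|---|---|---|---|
| 400 | ≤ 10% | 0.0980 | 0.1002 |
| 350 | – | 0.1048 | 0.1072 |
| 300 | 11.3% | 0.1132 | 0.1160 |
| 200 | 13.9% | 0.1386 | 0.1427 |

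The printed figures are Gaussian. The exact width at n = 400 exceeds 0.10 only for 188 to 212 events (47% to 53% AF).

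**2. Effect on the primary groups.** For 160/400 the Gaussian interval is 35.2–44.8% and the exact interval is 35.2–45.0%. For 40 to 360 events in 400, no limit differs by more than 0.43 percentage points.

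**3. The 4.1 rule at 0/n and n/n.** With p̂ = 0 or 1 the Gaussian half-width, 1.96 × √(p̂(1−p̂)/n), is 0. The interval is [0,0] or [1,1] for every n. Both bounds lie inside [0,1], so the switch does not fire. If BCa were run anyway, every resample would be identical and the limits undefined.

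At n = 20 the switch fires for 1 to 3 and 17 to 19 events, but not for 0 or 20. So 1/20 gets a bootstrap interval, while 0/20 is shown as certain.

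Exact intervals for comparison: 0/10 gives 0–30.8%, 0/20 gives 0–16.8%, and 10/10 gives 69.2–100%.

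The chance of such a cell is (1−p)ⁿ + pⁿ, which is the same for AF of p and 1−p:

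| n | AF 10% | 20% | 30% | 40% | 50% |
|---|---|---|---|---|---|
| 10 | 35% | 11% | 2.8% | 0.6% | 0.2% |
| 20 | 12% | 1.2% | 0.08% | <0.01% | <0.01% |

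**4. Coverage of the 4.1 rule.** Coverage was computed by summing binomial probabilities over all x. Where the switch fires, the BCa limits come from the binomial bootstrap distribution with jackknife acceleration. Ranges show three ways of handling ties in the bias correction.

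| n | AF | 4.1 rule | Exact |
|---|---|---|---|
| 10 | 10% | 65% | 98.7% |
| 10 | 20% | 89% | 99.4% |
| 10 | 25% | 92.4% | 98.0% |
| 10 | 30% | 96% | 98.9% |
| 10 | 40% | 91–94% | 98.2% |
| 20 | 10% | 88% | 98.9% |
| 20 | 20% | 92.1–97.8% | 97.8% |
| 20 | 50% | 95.9% | 95.9% |
| 30 | 10% | 95.0% | 99.2% |
| 30 | 30% | 95.3–96.0% | 97.4% |
| 30 | 35% | 91% | 96.4% |

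The first row is almost wholly the zero cell: P(0/10) = 0.9¹⁰ = 0.349, and 1 − 0.349 = 0.651.

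**The case against.** The strongest reply is that the plan is already clear enough. A specific rule repeated in both documents overrides a section headed as general principles, so the five objectives get exact intervals. The subgroup sentences speak of the intervals for Objectives 1a and 1b, which points back to the exact ones, and the only method the protocol names after its 10.3 lead-in is exact. On that reading the zero-width interval never appears. Even on the other reading it needs small cells with AF near 0 or 1, and at mid-range AF it is rare (0.2% at n = 10, AF 50%).

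The width excess at n = 400 is also immaterial. On the plan's own 2600, 35% attrition and 50% overlap, and assuming an equal split with no inconclusive-only entrants, 2600 × 0.65 × 0.5 / 2 ≈ 422 per group are exclusive (exact maximum width 0.0975). About 1267 (845 + 422) enter each primary denominator (0.056).

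Most of this stands. The exact text very likely governs the objectives, the primary results are hardly touched, and how often a degenerate cell would arise is unknown. But the subgroup method rests on inference: the SAP contains an unrestricted rule that names proportions, and an analyst who applied it would be following the document. The failure of 4.1 at 0/n and n/n does not depend on which reading is preferred.

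**Conclusion.** The concern holds. SAP 4.1 conflicts with SAP 4.3 and with protocol 10.3.1 to 10.3.2, without an order of precedence, and the interval method for subgroups is not pre-specified.

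For the full primary groups the consequence is negligible, and the target of 400 per group is not undermined. For subgroups it is conditional. If 4.1 is applied, cells with 0/n or n/n are reported without uncertainty, and coverage can fall well below 95% in small cells with AF near 0 or 1. Elsewhere the shortfalls are smaller or absent, and some depend on the BCa variant. The subgroup magnitudes rest on assumed cell sizes of 10 to 30 and assumed AF proportions.

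Separately, the shortfall widths in SAP 1.3 understate the exact ones by 0.3 to 0.4 percentage points. This should be corrected in the SAP, but it does not threaten the main results.

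**What to change.** - In SAP 4.1, state that the exact (Clopper-Pearson) interval is used for every observed proportion, covering Objectives 1a to 2c and all their subgroups. Delete the Gaussian/BCa rule for these.
- Keep a normal-type interval only for estimates pooled over multiple imputations (the EEAS sensitivity analyses in SAP 3 and the methods in SAP 4.6). Those have no single integer count, so an exact interval cannot be formed.
- Say which of the two applies to Objective 2a. It is analysed in the EEAS, where missing questionnaires may be imputed, yet SAP 4.3 assigns it an exact interval.
- Restate the worst-case widths in SAP 1.3 on the exact method: 0.1002 (10.0%) at 400, 11.6% at 300 and 14.3% at 200.

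The cost is SAP wording only, with no change in sample size. Exact intervals are mildly conservative (about 96% to 99% coverage in the small cells examined), and the stated widths become slightly less favourable.
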